4.2 Statistical and Analytical Methods

4.2.1 Analysis Populations and Analysis Groups

Population of Patients Enrolled [EP]

The population of patients enrolled comprises all patients who voluntarily sign and date an informed consent prior to inclusion into the study and data were captured in the eCRF.

Target Population [TP]

Patients will be included if the following applies:

- Age at least 18 years
- Confirmed CHC with genotype 1 and/or 4 only, receiving combination therapy with the interferon-free ABBVIE REGIMEN \pm RBV. The prescribed ABBVIE REGIMEN needs to be known.
- Have voluntarily signed and dated an informed consent prior to inclusion into the study
- Must not be participating or intending to participate in a concurrent interventional therapeutic trial

Core Population [CP]

The core population is defined as all patients of the target population (TP) (definition see above), who are adequately treated according to the standard of care and within local label recommendations for their specific disease characteristics (cirrhotic status, genotype). The following patients will be excluded from the CP:

- Patients with unknown fibrosis status
- Cirrhotic patients with genotype 1a not receiving ribavirin
- Patients with genotype 1 for whom 2DAA instead of 3DAA is prescribed
- Patients with genotype 4 not receiving RBV

Non-Core Population [NCP]

Patients in the TP who are not in the CP.

Core Population with Sufficient Follow-up [CPSFU {12, 24}]

In addition, the core population with sufficient follow-up data regarding SVR12 or SVR24, respectively, is defined as all CP patients,

- who have evaluable HCV RNA data ≥ 70 days or >126 days, respectively, after the last actual dose of the ABBVIE REGIMEN
- or a HCV RNA value ≥ 50 IU/mL at the last measurement post-baseline
- or had HCV RNA <50 IU/mL at the last measurement post-baseline, but no HCV RNA measurement ≥ 70 days or >126 days, respectively, after the last actual dose of the ABBVIE REGIMEN due to reasons related to safety (e.g. dropped out due to adverse event) or virologic failure (e.g. virologic failure such as relapse is reported in the electronic case report form (eCRF) but date and value of the corresponding HCV RNA test is missing).

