This means only (1) patients who had virological response at their last on-treatment or post-treatment measurement, but had no post-treatment HCV RNA measurements ≥ 70 days or >126 days, respectively, for reasons not related to safety or effectiveness (e.g. lost-to-follow-up or patient not willing to perform an additional HCV RNA test ≥ 70 days or >126 days post-treatment, respectively) and (2) patients who had no post-baseline HCV RNA measurements for reasons not related to safety or effectiveness, and (3) patients with missing end of treatment date for reasons not related to safety or effectiveness, will be excluded from this analysis.

Safety population [SP]

The safety population is defined as all enrolled patients who received at least one dose of the ABBVIE REGIMEN. The prescribed ABBVIE REGIMEN needs to be known.

EP and TP analysis groups

The EP/TP analysis groups are defined according to the patient's fibrosis status and genotype/subtype and standard summaries are structured as follows:

- Total (regardless of cirrhosis status)
 - (1) Total (regardless of genotype)
 - (2) G1 (Total)
 - (3) G1a (including mixed G1 subtypes and patients with G1 unknown subtype)
 - (4) G1b
 - (5) G4 (non-G1)
 - (6) Other/unknown genotype (*only for EP*)
- Patients with cirrhosis
 - (7) Total (regardless of genotype)
 - (8) G1 (Total)
 - (9) G1a (including mixed G1 subtypes and patients with unknown G1 subtype)
 - (10) G1b
 - (11) G4 (non-G1)
 - (12) Other/unknown genotype (*only for EP*)
- Patients without cirrhosis
 - (13) Total (regardless of genotype)
 - (14) G1 (Total)
 - (15) G1a (including mixed G1 subtypes and patients with unknown G1 subtype)
 - (16) G1b
 - (17) G4 (non-G1)
 - (18) Other/unknown genotype (*only for EP*)
- Patients with unknown fibrosis status
 - (19) Total (regardless of genotype)
 - (20) G1 (Total)
 - (21) G1a (including mixed subtypes and patients with unknown subtype)
 - (22) G1b
 - (23) G4 (non-G1)
 - (24) Other/unknown genotype (*only for EP*)

(HCV genotypes will be combined as follows: G1 [total], G1a*, G1b, G4 [non-G1]. * includes mixed or other G1 subtypes and patients with unknown G1 subtypes.

Most recent stage of liver fibrosis will be categorized as follows: No cirrhosis/Transition to cirrhosis, Cirrhosis. Only one method should be selected by the physicians to report stage of fibrosis. Nevertheless, if there are multiple answers the following priority will be used:

1. Biopsy,
2. Non-invasive,
3. Clinical/best guess.

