EoT	Actual EoT	Study day of last dose# (28 days prior to last dose - 7 days post last dose)
Post Treatment	12 weeks (SVR 12 window)	\geq 70-126 days post last dose
	24 weeks (SVR24 window)	127-210 days post last dose
	48 weeks\$	> 210 days post last dose

[^]values must also be \leq 7 days post last dose

\geq study day 2

*RVR = rapid virological response

\$ Please note that this time window is not specified in the study protocol, but added to consider possible relapse after day 210 in the analysis of the relapse rate. Analyses of SVR48 are not planned.

All reported safety laboratory test results will be assigned to one of the time points using the time windows specified in the table below.

Table 3 - Analysis Time Windows for Safety Laboratory Data

Phase	Time point	Time Window
Pre-Treatment	Baseline	Last value prior to start of study treatment (i.e. \leq study day 1)
Treatment Weeks	4 (day 29)	Study day during treatment period (Study day 1 = first treatment day)
	8 (day 57)	15 – 42 [^]
	12 (day 85)	43 – 70 [^]
	16 (day 113)	71 – 98 [^]
EoT	Actual EoT	Study day of last dose# (28 days prior to last dose - 7 days post last dose)
Post Treatment	4 weeks (28 days post last dose)	8– 56 post last dose
	12 weeks (84 days post last dose)	57 – 126 days post last dose
	24 weeks (168 days post last dose)	127 – 252 days post last dose
	48 weeks (336 days post last dose)\$	253 – 420 days post last dose

[^]values must also be \leq 7 days post last dose

\geq study day 2

\$ Please note that this time window is not specified in the study protocol, but added to consider possible reported values.

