4.2.7 Analyses of the Objectives

4.2.7.1 Primary Effectiveness Variable

The primary objective of this study is to estimate the SVR12 rates in HCV patients treated according to the ABBVIE regimen.

Therefore the simple percentage of patients achieving SVR12 (for definition see section 4.1.1) will be calculated and a two-sided 95% confidence interval (CI) of the percentage will be computed based on the Wilson's Score method.

The primary effectiveness analysis on clinical outcomes will be performed on all patients in the CP stratified by genotype and cirrhosis status and overall.

In the framework of sensitivity analyses the primary analyses will be repeated for the CPSFU. Furthermore, the SVR12 rates will be also determined for all patients of the NCP.

An overview of Tables is given in Table 7.

The layouts of the tables mentioned above are provided in Part II of the SAP (Table Shells).

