4.2.7.2 Secondary Variables

4.2.7.2.1 Secondary Effectiveness Variables

Response

For the other response rates (i.e. SVR24, EoT response rate, relapse rate, viral breakthrough), the simple percentage of patients and a two-sided 95% confidence interval (CI) of the percentage will be computed (based on the Wilson's score method) as well. The EoT response rates will be reported for CP and the SVR24 rates will be reported for the respective CPSFU, stratified by genotype and cirrhosis status and overall. The relapse rates will be estimated stratified by SVR window (i.e. during SVR12 window=relapse₁₂, during SVR24 window=relapse₂₄, after SVR24

window=relapse_{late}) and stratified by genotype and cirrhosis status and overall in patients of the CP with EoT response who fulfilled the following criteria:

- completed treatment as defined previously,
- had at least one HCV RNA measurement ≥ 70 days post-treatment or was a treatment failure between EoT and 70 days post-treatment.

Viral breakthrough rates [defined as at least one documented HCV RNA <50 IU/mL followed by HCV RNA ≥ 50 IU/mL during treatment] will be estimated overall and stratified by genotype and cirrhosis status in all patients of the CP, who have at least one undetectable or unquantifiable, on-treatment HCV RNA measurement and at least one on-treatment or EoT measurement thereafter.

Non-Response

In another table, the numbers and the percentages of the SVR12 non-responder categories and responder will be summarized for CP patients, overall and stratified by genotype and cirrhosis status. The following SVR12 non-response categories will be considered:

- On-treatment virologic failure (breakthrough [defined as at least one documented HCV RNA <50 IU/mL followed by HCV RNA ≥ 50 IU/mL during treatment] or failure to suppress [each measured on-treatment HCV RNA value ≥ 50 IU/mL])
- Relapse (defined as HCV RNA <50 IU/mL at EoT followed by HCV RNA ≥ 50 IU/mL post-treatment and completed treatment as defined previously)
- Death and none of the above
- Premature study drug discontinuation with no on-treatment virologic failure and none of the above
- Insufficient virological response, other than those mentioned above (patients for whom insufficient virological response was reported, or who had HCV RNA ≥ 50 IU/mL post EoT) and none of the above
- Missing SVR12 data and/or none of the above criteria

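### SVR24 is reported in a population that keeps documented failures but drops responders not re-sampled after day 126, so the rate tends to be too low

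*SAP*

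**What the plan says.** SAP 4.2.7.2.1 gives end-of-treatment response for the core population (CP), but for the later time point it says that "the SVR24 rates will be reported for the respective CPSFU". For SVR12, SAP 4.2.7.1 uses the CP as primary and adds: "In the framework of sensitivity analyses the primary analyses will be repeated for the CPSFU".

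SAP 4.2.1 gives three routes into the CPSFU for SVR12 and SVR24:

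- an evaluable sample from day 70 on (for SVR12) or later than day 126 (for SVR24), counted from the final dose;
- "or a HCV RNA value ≥ 50 IU/mL at the last measurement post-baseline", with no condition on when that value was taken;
- a last value below 50 IU/mL where late data are missing because of safety or virologic failure.

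The same section then names those who are left out. The first group is "patients who had virological response at their last on-treatment or post-treatment measurement, but had no post-treatment HCV RNA measurements" in the relevant period, where the cause has nothing to do with safety or effectiveness. Loss to follow-up and refusal of a further test are the examples given.

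The SVR24 window in SAP Table 2 is "127-210 days post last dose". SAP 4.2.3 allows flanking and backward imputation and counts any value still missing as failure. SAP 4.2.2 leaves all HCV RNA sampling to the physician. The schedules in both documents list HCV RNA at an SVR24 visit, but only data that routine practice happens to produce are collected.

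**The concern.** Membership of CPSFU24 is decided partly by the outcome it is meant to measure. A documented failure stays in the denominator without any late sample. A week-12 responder who is not tested again leaves both numerator and denominator. Imputation cannot bring that patient back, because both the flanking and the backward rule need a later value and there is none.

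The main thing SVR24 adds to SVR12 is information on whether the response lasts. If the SVR24 rate falls because cured patients were not re-tested, a reader may take the drop for late relapse. Nothing in either document warns of this selection. Protocol 9.9 says only that missing HCV RNA data can lead to underestimation of SVR. Protocol 9.7.1 defines the CPSFU around the 70-day rule alone, and Protocol 9.7.3.2 does not list SVR24 as an effectiveness endpoint. The SAP added both the endpoint and the 24-week set.

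**Working it through.** The plan gives no SVR24 figure to reproduce, so the check computes what the entry rule does to a known rate.

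**Inputs**

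- p, the true response rate: not planned for this study. Assumed 90% to 98%, in line with the pivotal results in Protocol 7.1 (for example 92% and 96% in the trial in cirrhosis).
- a, the share of week-12 responders with a value after day 126: not in the documents. Assumed 30% to 100%.
- Study size: 50 to 55 patients (SAP 3.2).
- Intervals: Wilson score, as in SAP 4.2.7.2.1.

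**Step 1. Expected rate in CPSFU24, with no late relapse and no loss before day 70**

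All failures (1 − p) stay and a fraction a of responders stays:

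rate = p·a / (p·a + 1 − p)

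At p = 0.95:

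- a = 0.8: 0.760 / 0.810 = 93.8%
- a = 0.5: 0.475 / 0.525 = 90.5%
- a = 0.3: 0.285 / 0.335 = 85.1%

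Other true rates:

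| True rate | a = 0.9 | a = 0.7 | a = 0.5 |
|---|---|---|---|
| 98% | 97.8% | 97.2% | 96.1% |
| 96% | 95.6% | 94.4% | 92.3% |
| 94% | 93.4% | 91.6% | 88.7% |
| 90% | 89.0% | 86.3% | 81.8% |

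With a = 1 the formula returns p. With p = 1 it returns 100%. In both cases the bias is zero.

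**Step 2. In patients**

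Take 53 CP patients: 3 documented failures and 50 responders, of whom 25 are re-sampled and all 25 are still below 50 IU/mL.

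- True rate: 50/53 = 94.3%
- CPSFU24 as planned: 25/(25 + 3) = 25/28 = 89.3% (Wilson 72.8% to 96.3%)
- CP with missing as failure: 25/53 = 47.2%
- Paired row: 25/25 = 100%, Wilson lower limit 25/(25 + 1.96²) = 86.7%, with 25 responders not re-sampled

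**Step 3. Late relapse**

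If 1% to 2% of responders relapse late and are re-sampled at the same rate as the others, the bias is essentially unchanged. The sign can reverse if late relapsers are never re-sampled. With 2% early failures, 2% late relapse among responders and 90% of the other responders re-sampled, the estimate is 97.7% against a true 96.0%, or +1.7 points.

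**Step 4. Comparison with SVR12**

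Assume 4% documented failures, 10% of responders lost before day 70, and a = 0.7 among the rest:

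- SVR12 in CP (missing as failure): 0.96 × 0.90 = 86.4%
- SVR12 in CPSFU12: 0.864 / (0.864 + 0.04) = 95.6%
- SVR24 in CPSFU24: 0.864 × 0.7 / (0.864 × 0.7 + 0.04) = 93.8%

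With no relapse at all, SVR24 lies above one SVR12 rate and below the other.

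**Step 5. Does the planned relapse rate settle it?**

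SAP 4.2.7.2.1 estimates relapse in the SVR24 window among CP patients with end-of-treatment response who completed treatment and have at least one value from day 70 on, or failed before then. A value after day 126 is not required. Suppose that the 3 failures in Step 2 were on-treatment failures, that all 50 responders completed treatment, and that 1 of the 25 re-sampled had relapsed. The planned rate would be 1/50 = 2.0%, against 1/25 = 4.0% among those actually tested. Responders never tested again can count as non-relapsers.

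**The case against.** The strongest reply is that durability is already covered. The same section plans relapse rates by window, and SAP Table 2 adds a window beyond day 210 to catch late relapse. If SVR24 fell through selective sampling alone, those tables would show no matching events. That is a useful cross-check, but Step 5 shows why it does not replace a result in patients actually re-sampled.

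Other points stand and limit the concern:

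- The re-sampling shares are assumptions. An SVR24 visit is on the schedule, and at 80% re-sampling the bias is only 1.2 points. Even at 50%, the interval in Step 2 contains the true 94.3%.
- SVR24 is one secondary, descriptive endpoint in a study of 50 to 55 patients.
- The Table 7 output title reads CP/CPSFU, so a CP row may be intended. The table shells that would settle this are in Part II of the SAP, which is not among the documents reviewed.

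A reader might also infer more than the documents support:

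- **That SVR24 and SVR12 follow different missing-data rules.** They do not: SAP 4.2.3 applies one set of rules to all SVR analyses. The populations differ.
- **That SVR24 has no SVR12 counterpart.** CPSFU12 is a near comparator with a milder form of the same asymmetry, though the two sets still differ by the responders lost between the windows.
- **That every earlier failure is kept.** Only documented ones are. A CP patient who fails SVR12 solely because data are missing, with a last value below 50 IU/mL and an unrelated loss to follow-up, is excluded from CPSFU24.
- **That SVR24 must therefore fall below SVR12.** Step 4 shows it need not.

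**Conclusion.** The concern holds as a selection problem of moderate weight. The CPSFU24 rate understates the true SVR24 rate whenever there are documented failures and some responders are not re-sampled, provided re-sampling does not depend on late relapse. For true rates of 90% to 98% and re-sampling of 50% to 90%, the shortfall runs from 0.2 points (98.0% to 97.8%) to 8.2 points (90.0% to 81.8%). At this sample size it will usually be smaller than the width of the interval. The re-sampling share is the decisive unknown, and only the data can supply it.

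The difference between SVR24 and the primary SVR12 rate has no fixed sign and should not be read as late relapse. No output planned in the SAP text gives durability among responders who were actually tested again.

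**What to change.** 1. Add a paired durability row to the virological response table: among SVR12 responders with an HCV RNA value after day 126, the number and percentage still below 50 IU/mL with a Wilson interval. Beside it, give the number of SVR12 responders not re-sampled.
2. Keep the CPSFU24 rate, with a footnote that entry depends on outcome and that the rate tends to be too low when late sampling is incomplete.
3. Reconcile the population named for SVR24 in SAP 4.2.7.2.1 with the CP/CPSFU title in Table 7.
4. Do not make SVR24 in the CP with missing as failure the main result. In Step 2 it gives 47.2% against a true 94.3%, so it would largely measure who was not sampled.

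The cost is one or two table rows from data already collected. The paired row has a smaller denominator and so a wider interval, and it still assumes that the responders tested again resemble those who were not. The count of responders not re-sampled lets the reader judge that.

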#### **9.7.3.3 Statistical Methods for Analysis of Effectiveness Variables**

The simple percentage of patients achieving SVR12 will be calculated and an exact two-sided 95% confidence interval (CI) of the percentage will be computed based on the Wilson's Score method.

Corresponding methods will be used for other response rates (EoT response rate, relapse rate, viral breakthrough). The relapse rates will be estimated in patients of the CP analysis groups with EoT response and sufficient HCV RNA measurements post-treatment. Viral breakthrough rates will be estimated in all patients of the CP analysis groups, who have at least one undetectable HCV RNA measurement on-treatment and at least one on-treatment or EoT measurement thereafter.

Univariate logistic regression methods will be used to investigate the impact of the following explanatory covariates on SVR12:

- Key demographic information
- Mode of CHC infection
- HCV RNA level at baseline
- Most recent stage of liver fibrosis
- HCV genotype and subtype (if available)
- Type of treating institute
- Liver and/or CHC related co-morbidities
- Key clinical chemistry and hematology laboratory variables at baseline

Confidential Information

No use or disclose outside AbbVie is permitted without prior written authorization from AbbVie  
The Netherlands v 1.4 (26 March 2018). Protocol based on AbbVie shell protocol version 3.0 (22 April 2015) Page 37 of 65

- In treatment experienced patients only:
  - Most recent prior treatment for CHC
  - Outcome of most recent prior CHC treatment

Further details and additional covariates will be specified in the SAP.

These analyses will be of exploratory nature, data driven, and will be repeatedly performed for various CP Analysis Groups, since not each covariate might be predictive in each patient group. Logistic regression methods will also be used to investigate the impact of treatment adherence on SVR12.

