4.1.2 Secondary Parameters

The secondary effectiveness endpoints are:

- The percentage of patients with virological response (HCV RNA <50 IU/mL) at EoT (defined as last intake of ABBVIE REGIMEN or ribavirin)
- The percentage of patients with relapse (defined as HCV RNA <50 IU/mL at EoT followed by HCV RNA ≥50 IU/mL)
- The percentage of patients with breakthrough (defined as at least one documented HCV RNA <50 IU/mL followed by HCV RNA ≥50 IU/mL during treatment).
- Sustained virological response 24 weeks after EoT (SVR24, i.e. patients with HCV RNA < 50 IU/mL 24 weeks after EoT)
- The number and percentage of patients meeting each and any of the following SVR12 non-response categories:
 - On-treatment virologic failure (breakthrough [defined as above] or failure to suppress [each measured on-treatment HCV RNA value ≥50 IU/mL])
 - Relapse (defined as HCV RNA <50 IU/mL at EoT followed by HCV RNA ≥50 IU/mL post-treatment for subjects who complete treatment [not more than 7 days shortened])
 - Premature study drug discontinuation with no on-treatment virologic failure
 - Missing SVR12 data and/or none of the above criteria

Further secondary variables are:

- Type of treatment regimen (± Dasabuvir, ± RBV, intended and actual combination, dose and duration)
- Adherence
 - Percentage of the DAA dose taken in relation to the target dose of DAA (cumulative dose taken divided by target dose in percent)
 - Percentage of the RBV dose taken in relation to the target dose of RBV (cumulative dose taken divided by target dose in percent)
 - Percentage of missed RBV treatment days in relation to the target number of RBV treatment days
- Co-morbidities and concomitant medication
- Serious and non-serious adverse events and pregnancy occurrences

- Questionnaires on PROs: e.g. EuroQol 5 dimension 5 level (EQ-5D-5L) questionnaire and work productivity and activity impairment (WPAI) questionnaire prior to treatment initiation, at EoT as well as **12 and 24** weeks after EoT
- Healthcare resource utilization

No data will be imputed for any effectiveness or safety analyses except for the analyses of the HCV RNA endpoints and PRO questionnaires (if applicable). For further details see sections 4.2.3 and 4.2.7.2.2, respectively.

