4.2.2 Definition of Baseline and Visit Time Windows

This observational study covers three documentation periods, see Figure 1. An overview of data to be collected throughout the study is summarized in Table 1.

Table 1 - Data Documentation Schedule

Assessment/ Procedure (only available data to be collected; no diagnostic or monitoring procedures to be applied to the patients apart from those of routine clinical practice)	Baseline	Treatment Period			Post-treatment (PT) Period		
		On-treatment visits	Mid treatment visit for pts receiving 24 weeks of therapy	EoT ^b	Early PT visit	SVR 12 visit	SVR 24 visit
Informed Consent	X ^a						
Demographic information	X						
IL28B	X						
Relevant CHC disease characteristics	X						
Liver fibrosis stage	X						
CHC treatment history	X						
HCV genotype and subtype	X						
HCV RNA samples	X	X	X	X	X	X	X
Clinical chemistry and hematology	X	X	X	X	X	X	X
ABBVIE REGIMEN initiation documentation	X						
ABBVIE REGIMEN adherence		X	X	X			
Concomitant medication	X	X	X	X			
Relevant medical history, co-morbidities	X						
sAE, AE and pregnancy reporting	X	X	X	X	X ^c	X ^d	X ^d
For patients receiving RBV: Evidence, in accordance with local label, that female patient or female partner of male patient is not pregnant	X						
Patient questionnaires – WPAI, EQ5D-5L	X			X		X	X
Health care resource utilization	X	X	X	X			

Abbreviations: EoT = End of Treatment (at Week 12 or 24 or at premature discontinuation),

PT = Post-Treatment

a Written informed consent must be obtained before any data documentation in the eCRF

b Patients who prematurely discontinue should return to the site to document EoT data

c Tolerability documentation until PT week 4

d Pregnancy reporting for patients treated with DAA +/- RBV

In accordance with the non-interventional nature of the study all HCV RNA measurements will be performed at the sole discretion of the physician and all HCV RNA measurements have to be entered into the eCRF. All recorded HCV RNA values will be assigned to appropriate time points (baseline, on-treatment visits, EoT visit, post-treatment visits) as follows:

Table 2 - Analysis Time Windows for HCV RNA

Phase	Time point	Time Window
Pre-Treatment	Baseline	Last value prior to start of study treatment (i.e. \leq study day 1)
On-treatment		Study day during treatment period ^{^#} (Study day 1 = first treatment day)
Treatment Week	4 (RVR*)	15 - 42 [^]

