4.2.3 Handling of missing data

No data will be imputed for any effectiveness or safety analyses except for the analyses of the HCV RNA endpoints and certain PRO endpoints. The discussion of missing data imputation for the PRO endpoints is included in section 4.2.7.2.2.

HCV RNA values will be selected for an RVR, EOTR and SVR analysis based on visit windows as defined in Table 2. When there is no HCV RNA value in a visit window based on defined visit windows, the closest values before and after the window, regardless of the value chosen for the subsequent and preceding window, will be used for the flanking imputation described below. For

analysis of RVR, EOT and SVR, if a subject has a missing HCV RNA value at a post-Day 1 visit but with undetectable or unquantifiable (LLoD or LLoQ \leq 50 IU/mL) HCV RNA levels at both the preceding value and succeeding value, the HCV RNA level will be considered undetectable or unquantifiable, respectively, at this visit for this subject. In addition, if a subject has an unquantifiable HCV RNA level at the preceding value and an undetectable HCV RNA level at the succeeding value, or vice versa, the HCV RNA level will be imputed as unquantifiable at this visit for this subject.

For analyses of RVR, subjects still missing a value for the visit after flanking imputation will be considered as a failure. For EoTR and SVR analysis, if there is no value in the appropriate window after flanking imputation but there is an HCV RNA value after the window, then it will be imputed into the EoTR or SVR window respectively. Subsequent to this flanking and backward imputation, if the HCV RNA value remains missing at a specific time point, then the subject will be considered as virological failure at this time point (i.e., not undetectable or unquantifiable).

If a subject starts another treatment for HCV, then all HCV RNA values for this subject measured on or after the start date of the new HCV treatment will be excluded from analyses. The subject will be considered a failure for summaries of viral response at all time points after the start of the new HCV treatment.

Due to the non-interventional nature of this study several different methods for determination of the HCV RNA value can be applied. For the purpose of the statistical analysis, a HCV RNA measurement is considered <50 IU/mL,

- if a PCR test was used

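### Relapse12, relapse24 and late relapse share one follow-up criterion, so unsampled patients count as non-events in the later windows and some relapses before day 70 fall in no window

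*SAP*

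**What the plan says.** SAP 4.1.2 names one relapse endpoint without a time window: "The percentage of patients with relapse (defined as HCV RNA <50 IU/mL at EoT followed by HCV RNA ≥50 IU/mL").

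SAP 4.2.7.2.1 turns this into three rates: "The relapse rates will be estimated stratified by SVR window". Relapse12 is relapse in the SVR12 window, relapse24 is relapse in the SVR24 window, and late relapse is anything after that. Table 2 in SAP 4.2.2 sets these windows at days 70-126, days 127-210 and beyond day 210. Each rate is a simple percentage with a Wilson 95% interval.

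One set of denominator criteria follows: core population, EoT response, completed treatment, and the patient "had at least one HCV RNA measurement ≥ 70 days post-treatment or was a treatment failure between EoT and 70 days post-treatment". No criterion refers to the window being reported.

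Four related provisions matter:
- Protocol 9.7.3.3 restricts relapse rates to patients "with EoT response and sufficient HCV RNA measurements post-treatment".
- In the same SAP paragraph, "the SVR24 rates will be reported for the respective CPSFU". SAP 4.2.1 gives that population its own follow-up rule, whose first criterion is data after day 126.
- SAP 4.2.2 notes that "all HCV RNA measurements will be performed at the sole discretion of the physician".
- Protocol 9.2.2 ends observation 24 weeks after treatment.

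**The concern.** Two groups of patients can be in a denominator with no possibility of being an event.

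The first is patients whose last sample precedes the window. A value on day 84 satisfies the follow-up criterion but says nothing about relapse after day 126. Sampling is discretionary, and the late window opens after planned observation has ended, so gaps in the later windows are to be expected.

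The second is patients who relapse on days 8-69. The criterion deliberately admits failures before day 70 (a term the SAP does not define), yet the first numerator window opens on day 70. Table 2 has no HCV RNA window between day 7 and day 70, although the documentation schedule lists HCV RNA at the early post-treatment visit.

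At stake is a declared secondary effectiveness endpoint. A late relapse rate of 0% could be printed with a fairly tight interval when few patients were tested, and the relapse table could disagree with the non-response table.

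**Working it through.** The plan states no relapse figure, so there is none to reproduce. I followed patients through the rules and then computed illustrative sizes.

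**Step 1: window coverage.** Days from last dose, SAP 4.2.2 Table 2: EoT -28 to +7; none for 8-69; relapse12 70-126; relapse24 127-210; late >210. Planned follow-up is 24 × 7 = 168 days, and 210 - 168 = 42, so the late window begins more than 42 days after planned observation ends.

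**Step 2: four patients, all treatment completers with EoT response.**

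| HCV RNA after EoT | In denominator? | Result as written |
|---|---|---|
| <50 on day 84, nothing later | Yes | Observed non-event in relapse12; unobserved non-event in relapse24 and late relapse |
| First re-sample <50 on day 150 | Yes | Non-event in relapse12, which is reasonable: the later negative shows no relapse by day 126 |
| ≥50 on day 30 and again on day 84 | Yes | Counted in relapse12 |
| ≥50 on day 30, no usable value from day 70 on | Yes, as an early failure | In no numerator window |

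The fourth case includes an early relapser who is re-treated, because SAP 4.2.3 excludes values from the start of new HCV treatment. The non-response table in 4.2.7.2.1 does count this patient as a relapse, because that category has no time window.

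**Step 3: limits with no event.** With 0 events in n patients the Wilson upper limit is z²/(n + z²), with z = 1.96 and z² = 3.84. Assumed: 45 qualifying patients out of the 50-55 expected (SAP 3.2). The documents give no sampling counts.

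| Informative patients | Upper 95% limit |
|---|---|
| 45 (as written) | 3.84/48.84 = 7.9% |
| 36 (80%) | 3.84/39.84 = 9.6% |
| 27 (60%) | 3.84/30.84 = 12.5% |
| 18 (40%) | 3.84/21.84 = 17.6% |
| 10 (late window) | 3.84/13.84 = 27.8% |

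**Step 4: one event in relapse24.** As written 1/45 = 2.2% (0.4-11.6%). On informative patients: 1/36 = 2.8% (0.5-14.2%), 1/27 = 3.7% (0.7-18.3%), 1/18 = 5.6% (1.0-25.8%).

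**Step 5: bias.** If sampling is unrelated to relapse, the expected reported rate is the true rate times the share sampled. For a true 5%: 5% × 0.8 = 4.0%, × 0.6 = 3.0%, × 0.4 = 2.0%. If every relapser is sampled on suspicion, the as-written rate is right and the sampled-only rate is too high (3.7% against 2.2% with 27 sampled).

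**Step 6: early relapses.** With two early relapsers who have no usable later value, and no other event, relapse12 is 0/45 (0-7.9%) as written and 2/45 = 4.4% (1.2-14.8%) if they are counted.

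**Step 7: coverage.** For true rate p and m patients sampled, I summed the Binomial(m, p) probabilities of every x for which the Wilson interval of x/45 contains p.

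| True window rate | Sampled out of 45 | Coverage as written |
|---|---|---|
| 1-5% | 5 to 36 | 95-100% |
| 10% | 36 | 97.0% |
| 10% | 27 | 94.1% |
| 10% | 18 | 85.0% |
| 10% | 5 | 41.0% |

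**The case against.** **A common denominator is a legitimate way to split one cumulative risk.** That stands as a design. But early relapses then still need a category, and patients not observed in the later windows still pull those rates down.

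**SAP 4.2.3 may already settle the unobserved patients.** A value missing after imputation is a virological failure, and for a re-treated patient: "The subject will be considered a failure for summaries of viral response at all time points after the start of the new HCV treatment". The imputation and missing-as-failure text is written for RVR, EoT response and SVR. Extended to relapse, it would make every unsampled patient a relapser, against a definition that requires HCV RNA ≥50 IU/mL. The SAP does not expressly exclude that reading, so a clarification is needed in any case.

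**Other outputs limit the damage.** The untimed relapse category in the non-response table and SVR24 on its own population mean that a reader does not depend on the windowed rates alone. This stands and lowers the severity.

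**Stronger readings that the documents do not support.**
- A reader might infer that relapse12 is diluted in the same way by patients first re-sampled after day 126. A later value <50 makes them sound non-events.
- A reader might infer that the intervals generally under-cover. On Step 7 they do not at true rates of 5% or less. Serious loss needs a rate near 10% with 40% or fewer sampled, and nothing in the documents supports 10% new relapse in a later window.
- A reader might infer that patients are counted twice. The SAP only leaves this unaddressed.

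**Conclusion.** The point holds for relapse24 and late relapse (unobserved patients as non-events) and, in all windows, for relapsers on days 8-69 with no usable later value. The later-window rates are biased downward unless relapsers are always sampled, and their limits do not reflect how many patients were tested. For relapse24 the effect is modest if most patients are sampled and material at 60% or fewer; the largest figures belong to the late window, which the SAP added only to capture possible relapses.

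All sizes rest on assumed counts: 45 qualifying patients, 18-36 informative for relapse24, 10 in the late window, and two early relapsers. The SAP table shells (Part II) are not among the documents, so a total row or window-specific denominators there cannot be ruled out. SVR12 is not affected. For a descriptive secondary endpoint this is minor to should-fix.

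**What to change.** In SAP 4.2.7.2.1:

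1. Report the 4.1.2 endpoint as one cumulative relapse rate: any HCV RNA ≥50 IU/mL from day 8 on after EoT response and before any new HCV treatment, on the present denominator. Define treatment failure before day 70 as HCV RNA ≥50 IU/mL on days 8-69.
2. Relapse12: keep the present denominator and count first values ≥50 on days 8-126. Requiring a sample on days 70-126 would drop later negatives but keep every early relapser; with five such negatives, 2/45 = 4.4% would become 2/40 = 5.0%.
3. Relapse24: count first values ≥50 on days 127-210, among patients not relapsed by day 126 who have a value on days 127-210 or a later value <50.
4. After day 210: list the cases and the number sampled, without a rate.
5. Count each relapser once, at the first value ≥50 by actual sample date, and show the number sampled in each window beside each rate.

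A footnote should explain one remaining mismatch. When the SVR12 window is empty and a later value exists, "then it will be imputed into the EoTR or SVR window respectively". A patient first found ≥50 after day 126 is therefore an SVR12 failure but a relapse24 or late case here.

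The cost is SAP wording and reprogramming of the relapse table, with no new data. Intervals widen. Relapse24 can be too high if sampling is prompted by suspicion, which is why the cumulative rate and the number sampled must stand beside it. If the table shells already work this way, only the text needs changing.
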